8.6.1. Listing and Presentation of individual PK data

The following presentations of patient plasma PK concentration data will be provided for each analyte for the PK Population using nominal times:

- Data listing, including patient, time point (actual, planned, deviation time), duration of actual sampling time to the last dose prior to the visit and treatment;
- Summary of prior-dose plasma PK concentrations-time data by treatment at each visit (population sample size (N), number of patients with available data (n), number of patients with imputed value (BLQ assigned to zero), mean, SD, coefficient of variation (%CV), median, minimum and maximum).

Where the %CV is calculated as:

- $\%CV = 100 * (SD/Mean)$.

9. SAFETY

The SAF will be used for all safety analyses. Safety will be assessed on the basis of AE reports, clinical laboratory data, extent of exposure and compliance, ECGs, physical examinations, and vital signs.

No inferential statistical testing is planned on the safety data, all data will be summarized and listed only.

9.1. Extent of Exposure

The duration of exposure during the treatment period will be expressed as the time in days from the first treatment through to last treatment day (inclusive). This is given by the following formula:

$$\text{Duration (days)} = \text{date last double blind dose} - \text{date first double blind dose} + 1$$

Duration of exposure will be summarized for the SAF using summary statistics for continuous variables.

All data will be listed.

9.2. Treatment Compliance

Study treatment compliance (%) will be calculated as the actual number of doses divided by the expected number of doses, multiplied by 100 and summarized by treatment group and study period (Run-in and Double-Blind Treatment).

These numbers will be determined by the number of tablets dispensed and returned unused by the patient. Where no treatment bottle is returned, and thus the actual number of doses is unknown, it will be assumed that the patient took all medication available in the bottle.

All data will be listed.

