3.9. Treatment Assignment and Blinding

Randomization will occur centrally using an interactive voice or web response system (IxRS) using central, stratified randomization. There are three treatment arms to which patients will be randomized in a 5:5:4 ratio:

- Vibegron 75 mg + placebo to match tolterodine ER 4 mg
- Placebo to match vibegron 75 mg + placebo to match tolterodine ER 4 mg
- Tolterodine ER 4 mg + placebo to match vibegron 75 mg

Randomization will be stratified based on the investigator-determined baseline categorization of OAB, referred to as OAB Type: Wet or Dry (as defined in the protocol inclusion and exclusion criteria), and Sex (Female vs. Male).

Enrollment will be capped based on OAB Dry criteria and sex as follows:

- Up to 25% of the patients enrolled may meet OAB Dry criteria.
- Up to 15% of the patient enrolled may be male.

A double-blind/masking technique will be used: vibegron and its matching placebo and tolterodine ER and its matching placebo will be packaged identically so that treatment blind/masking is maintained. The patient, the Investigator, and Sponsor personnel or delegate(s) who are involved in the treatment or clinical evaluation of the patients will not be aware of the treatment group assignments.

At the end of the study (including the 28-day Follow-up Period), the official, final database will be frozen and unblinded after medical/scientific review has been performed, and data have been declared final and complete. The Sponsor and [REDACTED] as designated representative will be granted access to the unblinded database in order to analyze the data. A clinical study report will be prepared after all patients complete the study.

IxRS should be used for emergency unblinding treatment assignment in the event that this is required for patient safety.

In the event that unblinding has occurred, the circumstances around the unblinding (e.g., date and reason) must be documented promptly, and the Sponsor notified as soon as possible. Only the Principal Investigator or delegate and the respective patient's code should be unblinded. Other Site personnel and Sponsor personnel directly associated with the conduct of the study should not be unblinded.

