3.10. Administration of Study Medication

Throughout the study, all Study Treatments will be taken by mouth once daily in the morning with 8 ounces of water. Study treatment may be taken without regard to meals.

During the Run-in Period, all patients will take placebo (1 tablet and 1 capsule) once daily for 2 weeks prior to the Baseline Visit. The Investigator will be aware that the Study Treatment during this period is placebo, however, the patient will NOT be told that the treatment administered during this period is placebo or that the patient needs to qualify to enter the randomized Treatment Period.

If a patient forgets to take Study Treatment in the morning, the missed dose should be taken as soon as possible on the same calendar day. However, if a dose is missed for an entire calendar day, the missed dose should not be taken on the following calendar day.

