5.8. Protocol Deviations

Protocol deviations are collected and agreed at the Protocol Deviation review meetings occurring prior to database lock (DBL); to evaluate protocol deviations considered to have a major impact on patient safety, efficacy or the validity of the study data. The protocol deviations are classified into 5 major categories and 1 minor category. The major categories are as follows:

- Major (Efficacy)
- Major (Efficacy Duplicate Patient)
- Major (Efficacy and Safety)
- Major (Safety)
- Major (Other)

Patients with major efficacy protocol deviations, which includes the 3 major categories above associated with efficacy, will be excluded from the PPS and PPS-I under the assumption that the deviation may have an impact on the efficacy analysis. Efficacy protocol deviation categories may include, but are not limited to the following:

- Inclusion/Exclusion Criteria Not Met
- Concomitant Medication (Prohibited Meds)
- Missed Study Visit
- Visit Out of Window
- Other (e.g. IP Compliance)
- Procedure Not Per Protocol

Other Major protocol deviation categories may include, but are not limited to the following:

- Informed Consent Issues
- IP Dispensation/Storage
- Lab Sample Issues (Missing/Not Analyzed etc.)
- AECI Not Reported

All major protocol deviations related to efficacy will be discussed during the BDRM, and decisions relating to exclusion for the PPS(-I) will be documented in the BDRM Report, finalized prior to unblinding.

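### Compliance counts an unreturned bottle as fully taken and counts only tablets, so the by-arm compliance summary is biased upward and may miss one of the two daily dose units

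*SAP*

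**What the plan says.** SAP Section 9.2 defines compliance as a percentage "calculated as the actual number of doses divided by the expected number of doses, multiplied by 100", summarised by treatment group and by study period (Run-in and Double-Blind Treatment). On the source of the counts it says: "These numbers will be determined by the number of tablets dispensed and returned unused by the patient". For a bottle that does not come back, it concedes that intake cannot be known and then sets this rule: "it will be assumed that the patient took all medication available in the bottle".

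Four other places bear on this:

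- Section 5.4 allows no imputation of missing safety data, apart from partial dates. Section 9 lists compliance among the safety assessments.
- Section 3.10 says of the run-in that "all patients will take placebo (1 tablet and 1 capsule) once daily for 2 weeks".
- Section 3.9 describes each arm as one product plus the placebo matching the other, for example "Vibegron 75 mg + placebo to match tolterodine ER 4 mg".
- Section 5.8 gives IP compliance as an example of what may be an efficacy deviation. Major efficacy deviations exclude a patient from the PPS and PPS-I.

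**The concern.** There are two separate faults in one derivation.

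**Unreturned bottles.** The SAP calls the number of doses unknown and then assigns the largest value possible. Any error in the doses credited from that bottle can only be upward. Elsewhere in its safety analysis the SAP resolves missing values against the drug: in Section 9.3 a missing causality assessment counts as related and a missing severity counts as severe. Here the missing value is resolved favourably, with no reason given and no count of the patients affected.

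**Tablets only.** If each daily dose is a tablet and a capsule, a tablet count sees half of it. In a double-dummy design, the half it sees is the placebo in whichever active arm carries its drug in the capsule. Unlike the bottle rule, this error has no fixed direction: it overstates intake when capsules are skipped and understates it when tablets are skipped.

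At stake is whether the compliance table can be trusted as a description of intake by arm and, if the percentage informs the blinded review, who stays in the per-protocol sets.

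**Working it through.** The SAP states no compliance figure, threshold, bottle size or non-return rate, so there is no planned figure to reproduce. The check applies the Section 9.2 formula to illustrative cases.

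**Inputs from the SAP**

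- Compliance = 100 × actual doses / expected doses (Section 9.2).
- Expected double-blind doses = 84: dosing runs from Day 1 to the day before the Week 12 visit, whose target is Day 85 (Table 3.11.1 and its footnote 20).
- Double-blind supplies are dispensed at Baseline, Week 4 and Week 8, that is, three times (Table 3.11.1).

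**Assumptions (not in the SAP)**

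- Each supply covers 28 doses, with overage varied from none (28) to 30 or 35 units.
- The share of doses in unreturned bottles, u, and the fraction of them truly taken, c, are varied.

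**1. No overage, returned supplies fully taken, nothing taken from the unreturned ones**

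- One supply unreturned: true (28 + 28 + 0)/84 = 66.7%; SAP rule (28 + 28 + 28)/84 = 100%.
- Two unreturned: true 28/84 = 33.3%; SAP rule 100%.
- Three unreturned: true 0/84 = 0%; SAP rule 100%.

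If half of one unreturned supply was taken, the true value is (56 + 14)/84 = 83.3%. If 80% was taken, it is (56 + 22.4)/84 = 93.3%. The rule gives 100% in each case.

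**2. Overage, one supply unreturned, the other two taken as expected**

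- 30 units per supply: (28 + 28 + 30)/84 = 86/84 = 102.4%.
- 35 units per supply: (28 + 28 + 35)/84 = 91/84 = 108.3%.

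**3. Arm level, no overage.** Overstatement in percentage points = 100 × u × (1 − c).

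- u = 5%: from 1.0 point (c = 80%) to 5.0 points (c = 0).
- u = 10%: from 2.0 points (c = 80%) to 10.0 points (c = 0).

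**4. Tablets against capsules.** A patient who takes every tablet but 0%, 50% or 80% of the capsules has capsule compliance of 0%, 50% or 80%. A literal tablet count gives 100% each time. Section 3.10 has one tablet and one capsule a day, and Section 3.9 has one active and one placebo product in each active arm. If the treatment-period forms match the run-in forms, one of the two active products is therefore the capsule, and that arm is assessed on its placebo tablet. This holds whichever product it is; the SAP does not say.

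**The case against.** The strongest reply is that the rule is explicit and prespecified, all compliance data are listed, and a specific rule in Section 9.2 may be meant to override the general one. Section 6.4 does leave missing data as missing only where nothing else is specified. That answers Section 6.4 but not Section 5.4, whose only exception is for partial dates. Nor does it give a reason for choosing the maximum.

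The word tablets may also be loose wording for all dosage units, since the formula speaks of doses. That is fair. In that case the correction is one of wording, but the SAP would still not say how two counts become one dose. The tablet-and-capsule statement describes the run-in only, so carrying it into the treatment period is an assumption.

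A reader might infer more than the SAP supports:

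- **That exposure is overstated.** It is not. Section 9.1 calculates duration from first and last dose dates, so bottle counts do not enter.
- **That the rule keeps non-compliers in the PPS and PPS-I.** Section 5.8 says only that IP compliance may be an efficacy deviation. No threshold is given and nothing ties that decision to the Section 9.2 percentage. Membership is settled at the blinded review, and site staff go through accountability discrepancies with the patient (Table 3.11.1, footnote 21). The effect is possible, not shown.
- **That compliance would reach 125%.** 35/28 = 125% is the score for one interval. Section 9.2 reports by study period, where 125% needs all three supplies unreturned: 105/84.
- **That patients who do not return bottles took fewer doses.** This is plausible, but the SAP gives no evidence for it and no non-return rate. Nor would a patient with one bottle missing necessarily score as fully compliant, because shortfalls in the returned bottles still count.

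It is also true that compliance over accounted-for intervals stays optimistic if non-returners are indeed non-compliers. That is why the number of unreturned bottles has to be shown beside it.

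**Conclusion.** The point holds, as a minor one. Section 9.2 replaces an unknown intake with full intake, contrary to Section 5.4, and as written it leaves capsules out of the count. The bottle rule biases the by-arm compliance summary upward. On the assumed supply sizes, one unreturned supply can turn a true 66.7% into 100%, or give 108.3% for a patient whose other two supplies were taken as expected. The shift at arm level depends on a non-return rate that the SAP does not give; it is 1.0 to 5.0 points if 5% of doses are in unreturned bottles and between 80% and none of them were taken.

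The tablet point rests on two conditions: the treatment-period forms match the run-in forms, and the word is taken literally.

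Compliance is descriptive and untested. It can reach an efficacy result only through the PPS and PPS-I, which are supportive. The primary analyses on the FAS and FAS-I do not change.

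**What to change.** Amend Section 9.2 before unblinding:

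- Set intake from an unreturned bottle to missing and calculate compliance over the accounted-for intervals, with the expected doses restricted to the same intervals. The current rule may be shown as a second version.
- Report the number of patients with at least one unreturned bottle, by arm and study period.
- Count tablets and capsules separately, or define a dose as taken only when both units are accounted for.
- State that a bottle not returned is not evidence of compliance if compliance is used in PPS or PPS-I decisions at the blinded review.

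The cost is a paragraph of SAP text and one derivation. The downside is that some patients will have compliance based on partial data.

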9.3. Adverse Events

AEs will be coded using MedDRA version 20.0 or later.

All reported AEs (whether treatment emergent or not) will be included in by-patient AE listings. The AE listing will have a column indicating if the onset of the AE by period. Sorting will be by country, site, patient, date of event, SOC, PT and then verbatim description.

An adverse event is any untoward medical occurrence in a patient or clinical investigation patient, temporally associated with the use of a medicinal product, whether or not considered related to the medicinal product.

An AE will be considered treatment emergent (TEAE) if it begins or worsens in severity after the first dose of the double-blind Study Treatment through 28 days after the last dose of Study Treatment, or the date of initiation of another investigational agent or surgical intervention or rollover to the extension study, whichever occurs first. Partial AE start dates will be imputed as detailed in [Section 6.4](#).

A Serious Adverse Event (SAE) is any untoward medical occurrence that:

- Results in death
- Is life-threatening
- Requires inpatient hospitalization or prolongation of existing hospitalization
- Results in persistent or significant disability/incapacity
- Is a congenital anomaly/birth defect
- Is another medically important condition

In addition, any illnesses reported before starting active treatment or AE meeting the criteria of seriousness (as defined above) and considered to be possibly related (according to the Investigator) to any study-specific procedure (e.g., laboratory testing procedure, liver biopsy) must be reported as an SAE.

Summary tables will be based on treatment emergent adverse events (TEAEs). The incidence of TEAEs will be presented using counts and percentages of patients with TEAEs and tabulated by SOC and PT. SOC will be sorted in descending frequency and PT within SOC will be sorted by descending frequency based on the incidence across patients overall. If a patient has multiple occurrences (start and stop) of an event associated with a specific SOC or PT within a SOC, a patient will only be counted once in the incidence count for the SOC or PT within SOC respectively.

An overall summary table of AEs by treatment group will be presented detailing the number and percentage of patients, and number of events for the following categories:

- At least one TEAE;
- At least one Treatment-Related TEAE;
- At least one Grade ≥ 3 TEAE;
- At least one Grade ≥ 3 Treatment-Related TEAE;
- At least one Serious TEAE;
- At least one Serious Treatment-Related TEAE;
- At least one TEAE leading to Discontinuation from Study Medication;

- At least one TEAE of Clinical Interest;
- At least one Treatment-Related TEAE of Clinical Interest

The incidence of all TEAEs by SOC and PT will be presented for the following:

- All TEAEs;
- Treatment-Related TEAEs;
- TEAEs with Grade ≥ 3 ;
- Serious TEAEs;
- Serious TEAEs with Grade ≥ 3 ;
- Treatment Related Serious TEAEs;
- TEAEs leading to Discontinuation from Study Treatment;
- Non-Serious TEAEs $\geq 5\%$ Threshold
- Non-fatal TEAEs
- Hypertension TEAEs by Pre-existing Hypertension (Yes vs No) and Baseline Hypertension (Yes vs. No). Hypertension TEAEs will be selected as any TEAE with Preferred Term of Hypertension.

Treatment listings will include the treatment arm, start and stop dates/times of the AE, and days on study relative to the day of first dose of study treatment.

A Treatment related AE is defined as an AE for which the investigator classifies the AE as being related to study treatment. To be conservative, the summary table will include events where the relationship to study treatment is missing. Missing severity for TEAEs will be counted as 'Severe'.

For the Non-Serious TEAEs $\geq 5\%$ Threshold, it will include adverse events if the event occurs at an incidence of greater than or equal to 5% in any treatment arm. No rounding is allowed. If an adverse event occurs at an incidence of 4.8%, for example, the incidence will not be rounded up to 5% for the purposes of this table.

Treatment Emergent Adverse Events of Clinical Interest (AECI) and Treatment-Related TEAEs of Clinical Interest will also be summarized by SOC and PT. Adverse Events of Clinical Interest for this study include:

- Potential Major Adverse Cardiac and Cerebrovascular Events (MACCE), which will be adjudicated by an independent external expert clinical adjudication committee (CAC) into the following categories according to the definitions in the CAC Charter:
 - Death or any event with fatal outcome
 - Myocardial infarction / Heart Attack
 - Cerebrovascular Accident / Stroke

- Hospitalization for Unstable Angina / Chest Pain
- Hospitalization for Heart Failure
- Coronary revascularization / Angioplasty / Stent
- Hypertension: An adverse event of hypertension should be reported and will be an AECI as follows:
 - For patients without hypertension (average SBP <140 mmHg, DBP <90 mmHg) at baseline, at two consecutive visits, the average of three systolic blood pressure (SBP) \geq 140 mmHg or diastolic blood pressure (DBP) \geq 90 mmHg (or both); at 2 consecutive visits in patients who were not hypertensive at baseline; or,
 - For patients with hypertension at baseline, an increase compared to baseline at 2 consecutive visits in the average of three SBP by \geq 20 mmHg OR DBP by \geq 10 mmHg;
 - Initiation of, or increase in dose of, medication for treatment of hypertension in any patient.
- Adverse events consistent with orthostatic hypotension as confirmed by orthostatic vital signs.
- Adverse events suggestive of cystitis or urinary tract infection.
- Elevated AST or ALT lab value requiring that study drug be temporarily withheld or permanently discontinued (see [Section 8.6.1](#) and Section 8.6.2).

The following additional listings will be provided:

- Listing of deaths
- Listing of Serious TEAEs
- Listing of non-treatment-emergent SAEs
- Listing of TEAEs leading to withdrawal or temporary withdrawal of study treatment
- Listing of all AEs with a flag for TEAEs and onset (Prior = prior to first dose of single-blind medication, Run-in = on or after first dose of single-blind medication but prior to first dose of double-blind medication, or Treatment = on or after first dose of double-blind medication.)

A summary of all TEAEs by maximum intensity (mild, moderate, severe, life-threatening, death), SOC, and PT will be presented, where the maximum intensity per patient will be counted at each level of summarization. In addition, a summary of all TEAEs by relationship to study treatment (related, not related), SOC and PT will be presented, where all relationships to study treatment per patient will be counted at each level of summarization. A summary of all TEAEs by PT occurring in at least 2% of patients in the

vibegron arm and greater than the placebo arm will be created and sorted by descending frequency in the vibegron arm.

A listing of all Medical History and pre-double-blind treatment adverse events with coded preferred terms belonging to the standard MedDRA query of hypertension will be created.

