17. At Week 8, the Urine Dipstick will only be performed if clinically indicated (e.g., symptoms of urinary retention or urinary tract infection).

18. Urinalysis will be performed only if the urine dipstick tests positive for the presence of leukocytes, nitrites, or blood cells, and will be performed by the central lab.

19. Urine beta-human chorionic gonadotropin (β -hCG) will be tested for women of childbearing potential only.

Dosing/Drug

20. Dosing will occur every day from the Witnessed Dose on the day of the Run-in Visit through the day before the Week 12 Visit.

21. Study Treatment bottles should be returned by the patient at each visit. Clinic staff will perform accountability and review any discrepancies with the patient during the visit.

22. All patients will take their dose of Study Treatment on the day of the Run-in and Baseline Visits at the site as a witnessed dose. The date and time of Study Treatment dosing will be recorded

Pharmacokinetics Subset Only

23. PK samples for Population PK Analysis will be collected from a subset of patients (approximately 30% of enrolled patients) at selected sites. Pre-dose blood samples will be collected at Week 4, Week 8, and Week 12. PK samples should be collected during the clinic visit after all other study assessments have been completed.

24. The date and time of the last dose of Study Treatment prior to PK sampling will be recorded.

Follow-up/Unscheduled

25. Unscheduled Visits and the specific procedures performed at these visits will be determined by the Investigator, as clinically indicated. The procedures indicated in the Schedule of Activities will be performed at these visits, as clinically indicated, based on the purpose of the visit (e.g., follow-up for an adverse event or abnormal laboratory test, study treatment dispensation). The reason for the visit will be captured in the source documents.

26. For Patients who do not enroll into the optional extension study (RVT-901-3004) or patients who withdraw from the study for any reason, a Follow-up Visit should be performed approximately 28 days after the last dose of Study Treatment on Study Day 113 or approximately 28 days after a patient's Withdrawal from the study. When a patient withdraws from the study prior to study completion, all applicable activities scheduled for the Week 12 Visit should be performed at the time of withdrawal.

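### The TEAE window closes at any surgical intervention, even while the patient is still taking double-blind treatment

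*SAP*

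**What the plan says.** SAP Section 9.3 defines a treatment-emergent event as one that "begins or worsens in severity after the first dose of the double-blind Study Treatment through 28 days after the last dose of Study Treatment". It then adds three earlier end points: "or the date of initiation of another investigational agent or surgical intervention or rollover to the extension study, whichever occurs first". Neither Section 9.3 nor any other part of the SAP defines surgical intervention, limits it to an indication, or ties it to the end of dosing.

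The same section bases its adverse event summary tables on TEAEs. For the events of clinical interest it says: "Treatment Emergent Adverse Events of Clinical Interest (AECI) and Treatment-Related TEAEs of Clinical Interest will also be summarized by SOC and PT". One adjudicated category on that list is "Coronary revascularization / Angioplasty / Stent".

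Events outside the window still reach the listings: "All reported AEs (whether treatment emergent or not) will be included in by-patient AE listings". There is a listing of deaths and a "Listing of non-treatment-emergent SAEs".

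On dosing, footnote 20 to the schedule in Section 3.11 says: "Dosing will occur every day from the Witnessed Dose on the day of the Run-in Visit through the day before the Week 12 Visit".

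**The concern.** A treatment-emergent window should at least cover the time on treatment. This one can close while treatment is still being taken. Of the three added end points, rollover cannot do this within the study, because Section 3.6 offers the extension only after the Week 12 Visit. An operation can fall on any day of the 12 weeks.

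At stake is the accuracy of the adverse event tables. Section 9.3 reports counts and percentages of patients. An excluded event lowers the numerator, while the patient stays in the Safety Set denominator. The clinical-interest list shows how the rule could act on events that matter. If a coronary revascularization counts as a surgical intervention, a stroke or heart failure admission that starts later on study drug would not enter the table of clinical-interest TEAEs.

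**Working it through.** The plan gives no figure on this point to reproduce. The check has three parts: the text, a day count, and a comparison with the SAP's other conventions.

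**Text.** The end of the window is the earliest of four dates:

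- last dose + 28 days;
- start of another investigational agent;
- surgical intervention;
- rollover to the extension study.

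Because the earliest date applies, an operation during dosing overrides the last-dose rule. The tables that then lose a later event are the overall summary, the SOC/PT tables (all, related, Grade 3 or higher, serious, leading to discontinuation), the clinical-interest and hypertension tables, and those by maximum intensity, by relationship and at the 2% threshold. The listing of events leading to withdrawal is also restricted to TEAEs. A non-serious post-operative event that led to stopping study drug would therefore be found only in the listings of all adverse events.

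**Day count.** The Week 12 Visit is on Day 85 and dosing runs to the day before, so the last dose is on Day 84. The full window ends on Day 84 + 28 = Day 112. For surgery on Day d in a patient who keeps dosing:

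- on-drug days lost = 84 − d
- window days lost = 112 − d

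| Surgery (assumed day) | On-drug days lost | Window days lost | Share of 112 |
|---|---|---|---|
| Day 15 | 84 − 15 = 69 | 112 − 15 = 97 | 87% |
| Day 29 | 84 − 29 = 55 | 112 − 29 = 83 | 74% |
| Day 57 | 84 − 57 = 27 | 112 − 57 = 55 | 49% |

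Section 6.3 puts the last dose on Day 85, which shifts these counts by one day and changes nothing of substance. A patient who rolls over loses less of the 28-day tail, because rollover closes the window anyway.

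**Other conventions in the SAP.**

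- Section 9.1 defines exposure as last double-blind dose − first double-blind dose + 1. For the Day 29 patient that is 84 − 1 + 1 = 84 days, 55 of them in a period from which no new event can be tabulated.
- The all-AE listing in Section 9.3 assigns onset to the treatment period from the first double-blind dose, with no surgical cut-off. The same event would carry a treatment-period onset and a negative TEAE flag.
- Section 9.3 handles missing relationship and missing severity conservatively, counting them as related and as severe. The surgical cut-off works in the opposite direction.

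**Scale, by assumption only.** The SAP gives no rate of surgery. If 1% to 3% of a 500-patient arm had an operation while dosing and continued, that is 5 to 15 patients. With operations spread evenly over 84 days, the mean loss is 84/2 = 42 on-drug days plus 28, or 70 of 112. The share of the arm's window time lost would be 0.01 × 70/112 = 0.6% to 0.03 × 70/112 = 1.9%. Patients who roll over would lower these figures.

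**The case against.** The best counter-argument is grammatical. The word investigational may govern both nouns, so that only an investigational agent or an investigational operation closes the window. Placing the phrase next to rollover fits that idea of a move to a different study intervention. On that reading a routine operation or a coronary stent closes nothing. This is possible, but the text does not say it, and a programmer has to derive a flag from the text.

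Second, on-drug time is lost only if patients stay on study drug after surgery. The SAP does not say whether they do, and the protocol is not at hand. If dosing stops at the operation, only part of the 28-day tail is lost. This stands as a condition on the size of the problem. It does not make the rule sound as written.

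Third, the excluded events stay visible. All adverse events are listed, with separate listings for deaths and for SAEs outside the window, and Section 9 plans no inferential testing of safety data. That is correct and limits the harm, but the summary tables would still be incomplete.

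A reader might infer more than this: that every safety table is affected, or that serious event rates in the sickest patients are biased down. The documents do not support either.

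- Laboratory, vital sign, PVR, exposure and compliance summaries do not use the TEAE window.
- Events that began before the operation remain TEAEs, and a patient already counted in a row for at least one event stays counted. What is lost is a later preferred-term entry, the count of events, or a patient's first event if it follows surgery.
- Nothing links an operation to the sickest patients, since an unqualified operation includes minor and elective ones.

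**Conclusion.** The point holds for the adverse event summary tables. As written, Section 9.3 lets an operation end the TEAE window during dosing, so events that begin or worsen afterwards on study drug are listed but not tabulated. For a patient dosing to Day 84, the loss is 69 on-drug days with surgery on Day 15 and 27 with surgery on Day 57.

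This rests on the literal reading of the phrase and on patients continuing study drug after surgery; the SAP settles neither. How many patients are affected cannot be derived from the SAP and is probably small. Few events would be needed to change a sparse row, such as a serious or adjudicated event. The direction is towards fewer counted events in each arm. A reader might infer a distorted comparison of vibegron with placebo, but nothing in the SAP shows that operations or later events would differ between arms. Whether an event on the day of surgery itself counts is also unclear.

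**What to change.** Before unblinding, add one sentence to Section 9.3: any adverse event with onset or worsening between the first and last double-blind dose is treatment emergent, regardless of surgery. If a surgical cut-off is kept, let it apply only after the last dose, define the type of surgery (including whether only investigational surgery is meant), and say how events on the day of surgery are classed.

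If the current definition must stay, add a summary table of all adverse events from first dose to last dose + 28 days regardless of surgery.

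The cost is the sentence and a change to the TEAE flag derivation. The downside is that a few post-operative events will be counted as TEAEs.
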